**The following scales will be piloted for our future RR&D Merit submission.**

1. The **MINI Mental State Examination (MMSE)** will be used to test for adequate cognitive function to participate in this study. This 11-question measure tests five areas of cognitive function: orientation, registration, attention and calculation, recall, and language. The maximum score is 30. A score of 23 or lower is indicative of cognitive impairment (Folstein et al., 1975).
2. **The World Health Organization Disability Assessment Schedule, 2nd Version (WHODAS 2.0)** will be used to measure functional status as relates to health (Üstün et al., 2010). The WHODAS 2.0 has been validated in the general population and amongst those with non-acute health conditions, and has a Cronbach's alpha of .96 (Saltychev et al., 2021)
3. We will measure resilience using the **Measure of Current Status Part A (MOCS)**, the first section of two-part Likert scale; participants' current self-perceived status and potential nonspecific effects of the intervention and alphas ranging from 0.71 to 0.89 (Antoni et al., 2006; Antoni et al., 2006a).
5. **The Quality of Life Scale (QOLS)** measures domains that diverse patient groups with chronic illness define as quality of life. The QOLS is a valid instrument for measuring quality of life across patient groups and cultures and is conceptually distinct from health status or other causal indicators of quality of life (Burckhardt & Anderson, 2003) Identity concerns will be assessed with the **Future Self-Continuity Questionnaire, (FSCQ)**, which measures an individual's sense of personal identity from the present to the future ([name] & Serper, 2019). This Likert scale questionnaire (responses between 0-6) is a 10-item self-report instrument that addresses three areas of future self-continuity: vividness, similarity, and positivity. The FSCQ has demonstrated high levels of reliability ( $\alpha=.85$ ) and validity.
6. Suicidal ideation and behavior will be measured with the **Suicide Behaviors Questionnaire- Revised (SBQ-R)**. In view of its moderate to strong reliability, its construct and face validity, its ease of administration and scoring, and its brevity, the SBQ is recommended as a brief screening instrument for suicidality for researchers and clinicians (Cotton et al., 1995).
7. **Questionnaire about the Process of Recovery (QPR)** is a 22-item scale designed to assess progress through the process of recovery. The QPR is a self-report questionnaire and items are designed to measure recovery. The survey asks participants to rate their agreement with statements on a 5-point Likert scale (0=strongly disagree, 5=strongly agree). This measure has demonstrated high reliability and validity (Neil et al., 2009).

The following assessments are conducted as part of admission to the Long-COVID Clinic at the JJPVAMC. Therefore, to eliminate repetitive measures from those recruited from the Long-COVID clinic, these assessments will be pulled from enrolled participants' CPRS charts. These assessments will only be pulled if they had been completed **less than or equal to 3 months** prior to enrollment in the study:

8. **COVID-19 Yorkshire Rehabilitation Scale (C19-YRS)** consists of 22 items with each item rated on an 11-point numerical rating scale from 0 (none of this symptom) to 10 (extremely severe level or impact). The C19-YRS is divided into four subscales (range of total score for each subscale): symptom severity score (0–100), functional disability score (0–50), additional symptoms (0–60), and overall health (0–10). The C19-YRS can be freely obtained under license from the University of Leeds(O' Connor et al., 2022).
9. **Patient Health Questionnaire- 9 (PHQ-9)** is the 9-item depression module from the full PHQ. Major depression is diagnosed if 5 or more of the 9 depressive symptom criteria have been present at least "more than half the days" in the past 2 weeks and 1 of the symptoms is depressed mood or anhedonia. As a severity measure, the PHQ-9 score can range from 0-27, since each of the 9 items can be scored from 0 (not at all) to 3 (nearly every day). An item was also added to the end of the diagnostic portion of the PHQ-9 asked patients who endorsed symptoms: "How difficult have these problems made it for you to do your work, take care of things at home, or get along with other people?" (Kroenke et al., 2001).

10. **GAD-7 Anxiety** is a valid and efficient tool for screening for GAD and assessing its severity in clinical practice and research (Spitzer et al., 2006).

If a participant does not have these measures previously completed in their medical chart and/or they are more than 3-months old, they will be conducted by the study staff following consenting procedures.

Test /Procedure:	Outcome	When:	# of times:
MINI Mental State Examination (MMSE)	Cognitive Function	Consent & baseline	1
The World Health Organization Disability Assessment Schedule, 2nd Version (WHODAS 2.0)	Functional Status as relates to health (primary outcome)	Consent & baseline, post- Mod 1, Post Mod 2,	3
Suicide Behaviors Questionnaire- Revised (SBQ-R)	Suicidal Risk/Behavior	Consent & baseline, post- Mod 1, Post Mod 2,	3
Measure of Current Status (MOCS)	Resilience	Consent & baseline, post- Mod 1, Post Mod 2,	3
The Quality of Life Scale (QOLS)	Quality of Life	Consent & baseline, post- Mod 1, Post Mod 2,	3
Future Self-Continuity Questionnaire, (FSCQ)	Identity Concerns	Consent & baseline, post- Mod 1, Post Mod 2,	3
GAD-7 Anxiety	Anxiety	Consent & baseline, post- Mod 1, Post Mod 2,	3
Patient Health Questionnaire- 9 (PHQ-9)	Depression	Consent & baseline, post- Mod 1, Post Mod 2,	3
COVID-19 Yorkshire Rehabilitation Scale (C19-YRS)	Long COVID Symptom severity	Consent & baseline, post- Mod 1, Post Mod 2,	3
Questionnaire about the Process of Recovery (QPR)	Progress through Recovery Process	Consent & baseline, post- Mod 1, Post Mod 2,	3

**Feasibility and acceptability metrics.** Feasibility will be tracked through 1) implementation ease - tracking the hours clinicians spend in preparation, delivery, and supervision with a target of 100 hours/ cycle (5 hours per group). 2) recruitment - tracking referrals and 3) attendance/retention - tracking the sessions Veterans attend. Our criteria for retention will be “adequate” if 60% attend at least 5 of the first 8 sessions (Module 1), 5 of the second 8 sessions (Module 2), and 10 of the total 16 sessions (Module 1 + Module 2). A similar strategy will be used for recruitment rates, with feasibility deemed “adequate” if at least 60% of Veterans approached for participation in the study agree. At the end of each session, we will ask veterans the following questions: “What did you like about this session?” “What did you not like about this session?” “Do you have any suggestions for improvement?” to gauge acceptability, feasibility, and appropriateness of each session.

Veterans will complete the AIM, IAM and FIM ( Weiner et al., 2017) prior to and after completion of the program. These are four-item measures of implementation outcomes (acceptability and feasibility of intervention and intervention appropriateness) that are often considered “leading indicators” of implementation success (Proctor et al., 2011). We will also track homework adherence by percent complete. Lastly, upon completion of all LCCR sessions we will ask the veterans’ additional questions to obtain *participants’ feedback on the group*. Responses will be de-identified and analyzed for future development and implementation purposes.

Test /Procedure:	Outcome	When:	# of times:
Acceptability of Intervention Measure (AIM) Weiner et al., 2017)	How acceptable or satisfactory is the LC-CR group is to Veterans	Pre-treatment, Post-treatment (Mod 1), Post treatment (Mod 2)	3
Intervention Appropriateness Measure (IAM) Weiner et al., 2017)	How is the perceived fit, relevance, or compatibility of LC-CR to Veterans	Pre-treatment, Post-treatment (Mod 1), Post treatment (Mod 2)	3
Feasibility of Intervention Measure (FIM) Weiner et al., 2017)	How easy is it to participate in LC-CR	Pre-treatment, Post-treatment (Mod 1), Post treatment (Mod 2)	3
Qualitative Interviews	Acceptability, Feasibility, and Appropriateness of Intervention to help identify other needed implementation strategies for future dissemination	Post-treatment (Mod 2)	1

**5.5.1 EMA Protocol (to be carried out at Minneapolis VA by [name] team):** Participants who opt-in to the optional EMA component of the study during the consent process will be scheduled to receive three different week-long bursts of daily surveys (one at baseline, mid-treatment, and end of treatment). Each survey will contain approximately 20 questions and will be delivered at the end of the day (at a personalized time). They are expected to take approximately 3 minutes to complete. The surveys do not contain any intervention component. Participants will receive links to these questionnaires via text message.

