## 3.0 Objectives

**Overall Goal:** To pilot a Long-COVID psychotherapeutic intervention, “Long-COVID and Recovery” (LC-CR) while collecting pilot data to assess its acceptability and feasibility.

**Aim 1:** Identify adaptations needed to optimize LC-CR for Veterans with Long-COVID through veteran and stakeholder consultation.

**Aim 2:** Identify possible benefits of LC-CR.

**Aim 3:** Inform development of a large scale RCT of LC-CR for Veterans with Long-COVID.

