### 3A) Significance

#### Long-COVID in the VA:

A recent VA-based *Nature* publication representing the largest cohort of Long-COVID patients studied to date (n= 73,435 non-hospitalized patients with COVID-19, 13,654 hospitalized patients with COVID-19 and 5 million other VA patients without COVID-19) reported on 6-month outcomes post-infection (Al-Aly et al., 2021). Long-COVID patients had an increased risk of death, use of health resources, and a substantial burden of health loss spanning multiple organ systems. Post COVID-19 VA patients also showed increased mental health problems including sleep disorders, anxiety disorders, trauma and stress-related disorders as well as used more opioid and non-opioid pain medications, antidepressants, and sedatives to treat these conditions (Al-Aly et al., 2021). The authors also found that the severity of initial COVID-19 infection predicted later Long-COVID symptom severity. A recently published report on one-year longitudinal follow-up data on hospitalized COVID-19 patients, noted statistically significant increases in anxiety or depression from the six-month to twelve-month time points (Huang et al., 2021). **These findings are critical to estimating the impact of Long-COVID on Veterans, who may have unique vulnerabilities due to increased incidence of trauma, physical, and psychiatric risk factors** (Marini et al., 2020; Na et al., 2021; Hill et al., 2021).

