## 5.2 Recruitment Methods

Long-COVID Patients will be recruited through recruitment from James J. Peters VAMC Long-COVID clinical program and clinician referrals. The Bronx had significantly higher rates of COVID-19 infection than other boroughs in New York City. Thus, recruitment of *up to 36 Veterans* is feasible within the 18-month timeframe.

**Limitations and Future Directions.** One potential issue may be the recruitment of Veterans with Long-COVID. However, a strength of the proposed study is it's involving telehealth, making it more appealing to participants and less prone to no-shows. We will also recruit from our in-house Long-COVID center and multiple existing national Long-COVID programs. While the JJPVAMC is diverse in race and ethnicity, our

study may still have a diversity limitation as it will be conducted in an urban northeast VAMC and may not fully generalize to other areas of the USA. Future studies should extend the findings across other VAMCs. During year 2 we will submit a Merit Award to complete the planned follow up study testing the final manualized version of LC-CR (developed in this SPiRE project) in a multi-site clinical efficacy RCT.

Veteran participants will be offered financial compensation for their participation based on completion levels of the following:

Research Procedure for LC-CR	Participant Compensation
Pre-Treatment Baseline Assessment	\$75
Post-Intervention Assessment (Mod 1)	\$75
Post-Intervention Assessment (Mod 2)	\$75
Post-Intervention Qualitative Interview (Mod 2).	\$75

You will also receive a \$50 bonus upon completion of each therapy module (after the first 8 sessions and after the second 8 sessions).

Participants who consent to enroll in the EMA portion of the research study will be compensated for their participation. The JJPVAMC will be responsible for compensating patients. Participants will be compensated per survey initiated (i.e., at least one question is answered). Participants can receive up to \$135 across all three week-long bursts of daily surveys.

At this time, we anticipate providing a maximum of \$135 per person for participating. Each burst listed below lasts for 7 days. The payment schedule is as follows:

- Burst 1, baseline: \$4 per daily assessment initiated
  - Maximum: \$28 for this burst
- Burst 2, mid-treatment: \$5 per daily assessment initiated
  - Maximum: \$35 for this burst
- Burst 3, end of treatment: \$6 per daily assessment initiated
  - Maximum: \$42 for this burst

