## **5.4 Inclusion/Exclusion Criteria**

Inclusion criteria include: (1) U.S. Veteran (2) Age 18-80 (3) Screened positive for Long-COVID (e.g., COVID-19 positive, diagnosed with a PCR test and/or an antibodies blood test, and symptoms lasting 1 month or longer after infection (4) Participation in VA Services the JJPVA (5) Sufficient clinical stability and readiness to participate in a group therapy as deemed by their VA Service provider,

Exclusion criteria include: (1) Active alcohol or opiate dependence requiring medically supervised withdrawal. (2) Active psychosis. (3) MINI Mental Status < 23 or inability to function in a group setting. (4) Those unable to operate telehealth platforms or other devices. (5) Unable to speak English. (6) Lack of capacity to consent. (7) Unable or unwilling to provide at least one contact for emergency purposes.

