## **5.5 Study Evaluations**

**Clinical Assessments and Schedule.** Patients will have been screened/diagnosed as a part of their local VAMC's Long-COVID Clinical Center. Interested eligible participants will enroll and undergo assessments at pre (consent & baseline), immediately post module 1 of therapy (after first 8 sessions) and immediately post module 2 of therapy (after second 8 sessions) via either in person, over the phone, or via HIPAA-compliant web platform VA Video Connect (VVC) (with Audacity audio recording software) with VA WebEx as a viable backup depending on the participant's preference/availability.

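### Baseline PHQ-9, GAD-7 and C19-YRS may be clinic chart scores up to 3 months old, which adds avoidable pre-treatment change of unknown sign to three non-primary outcomes

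*Protocol*

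**What the plan says.** Section 5.5 of the protocol schedules PHQ-9, GAD-7 and C19-YRS three times: at consent and baseline, after Module 1 and after Module 2. For these three scales only, it adds a rule. They are part of admission to the Long-COVID clinic, so "to eliminate repetitive measures from those recruited from the Long-COVID clinic, these assessments will be pulled from enrolled" participants' charts, provided they were completed no more than 3 months before enrolment. If the chart has no score, or if "they are more than 3-months old, they will be conducted by the study staff following consenting procedures".

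The other scales carry no such rule. These include WHODAS 2.0, which the schedule names as the primary outcome.

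The protocol (section 5.6) plans repeated-measures mixed models across time points. The SAP describes paired t-tests, or paired Wilcoxon tests, of pre-to-post change. Neither mentions the age or source of a baseline score. The SAP does not list its secondary outcomes; that these three scales are among them is inferred from their three-time-point schedule.

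**The concern.** The baseline value does not refer to the same moment for every Veteran, nor for every scale within one Veteran. A clinic recruit's WHODAS 2.0 is taken at enrolment, while the same person's PHQ-9 may be 3 months older. The limit runs back from enrolment, not from session 1, so any wait for a group to start adds to the age. The protocol describes the PHQ-9 criteria over the past 2 weeks, so an old score describes a different period from the start of treatment.

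Aim 2 is to "Identify possible benefits of LC-CR", and there is one group with no control. A chart baseline adds change that happened before session 1. Improvement in that period would look like benefit; worsening would hide benefit. The documents do not settle the direction. Eligibility sets no threshold on these scales and admits Veterans with "symptoms lasting 1 month or longer after infection", while section 3A cites a hospitalized cohort with "statistically significant increases in anxiety or depression from the six-month to twelve-month time points". The scales are being piloted for the later RCT application, so a distorted change score could carry forward into it.

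**Working it through.** The documents give no effect size, SD or power for these scales, so there is no stated figure to reproduce.

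**Inputs from the documents**
- Maximum score age at enrolment: 3 months, taken as 13 weeks (section 5.5).
- Treatment: 16 weekly sessions in two modules of 8 (section 5.1).
- Sample: "up to 36 Veterans" (section 5.2).
- Significance level: .05 (SAP), taken as two-sided.

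**Assumptions**
- Session 1 falls at enrolment.
- Untreated drift is 0.1, 0.2 or 0.3 SD of the scale over 13 weeks.
- The SD of the change score is 0.9 in the same units (range 0.7 to 1.3).
- The share of Veterans on chart baselines is 1, 0.5 or 0.25.

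**Step 1: share of the interval before treatment** = score age / (score age + treatment weeks)

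| Score age | To post-Module 2 | To post-Module 1 |
|---|---|---|
| 13 weeks | 13/29 = 45% | 13/21 = 62% |
| 6.5 weeks (assumed mid-window) | 6.5/22.5 = 29% | 6.5/14.5 = 45% |

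Section 2.0 also mentions twenty weekly sessions; on that count the first entry would be 13/33 = 39%.

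**Step 2: shift in mean change** = share on chart scores × drift
- All on 13-week-old scores: 0.1 to 0.3 SD.
- Half: 0.05 to 0.15 SD.
- A quarter: 0.025 to 0.075 SD.
- At 6.5 weeks each value halves.

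For scale, the 95% confidence half-width is t × SD/√n. At n = 36 this is 2.03 × 0.9/6 = 0.30 SD (0.24 at SD 0.7, 0.44 at SD 1.3).

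**Step 3: chance of p < .05 when LC-CR has no effect and drift is improvement that stops at enrolment.** Two-sided paired t-test, noncentrality = (mean shift/SD) × √n, with n = 36 and SD 0.9.

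| Chart share, score age | Drift 0.1 | 0.2 | 0.3 |
|---|---|---|---|
| All, 13 weeks | 9.9% | 25.4% | 49.4% |
| Half, 13 weeks | 6.2% | 9.9% | 16.3% |
| A quarter, 13 weeks | 5.3% | 6.2% | 7.8% |
| Half, 6.5 weeks | 5.3% | 6.2% | 7.8% |

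The 49.4% corner becomes 71% at SD 0.7, 27% at SD 1.3, and 32% with 22 pairs.

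**Step 4: the same drift continues through the 16 treatment weeks.** This adds drift × 16/13 = 0.123, 0.246 or 0.369 SD for everyone.

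| Baselines | Drift 0.1 | 0.2 | 0.3 |
|---|---|---|---|
| All fresh | 12.6% | 35.8% | 66.8% |
| Half on 13-week-old scores | 20.2% | 61.2% | 92.0% |

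**Step 5: drift in the other direction.** Here units are SDs of the change score. With a true change of 0.5, n = 36 and all on chart scores, power falls from 83% to 42% if Veterans worsened by 0.2 before enrolment.

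**The case against.** The strongest reply is that the effect is small beside the trial's main limit. With no control arm, pre-to-post change cannot be attributed to LC-CR with any baseline, and step 4 shows that fresh baselines alone could give 13% to 67% significant results under continuing drift. The paired test's null is no change, and drift is real change; the error lies in attribution. The large figures in step 3 need every Veteran at the 13-week limit, whereas 3 months is a maximum and section 5.3 also recruits through other medical providers. At a mid-window age with half on chart scores, the shift is 0.025 to 0.075 SD, well inside the confidence half-width.

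The rule is also reasoned: it spares repetition in a population with fatigue and poor concentration, sets a recency limit and has a fallback. The overall goal is acceptability and feasibility, with efficacy left to the RCT. The SAP is written in the past tense, so data collection may be over.

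Most of this stands as a limit on size. The all-chart figures are bounds, and the uncontrolled design matters more. It does not remove the point: the chart increment is separate from change during treatment, falls on three scales only, is not recorded or reported, and can be avoided by a procedure that staff already use.

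**Conclusion.** The concern holds. Following the plan as written puts pre-treatment change into the pre-to-post result for PHQ-9, GAD-7 and C19-YRS. That the rule exists and that the analysis ignores score age is certain from the text. Up to 45% of the interval to post-Module 2, and 62% to post-Module 1, can precede treatment if session 1 falls at enrolment.

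The effect on results cannot be determined, because drift, the SD of change and the share of chart baselines are not given. Under the assumed ranges it runs from negligible (5% to 8% significant results with a quarter on 13-week-old scores) to serious (10% to 49% with all). The direction is unknown. WHODAS 2.0, the scales without a chart rule and the feasibility and acceptability criteria are unaffected. This is a matter that should be corrected, not one that undermines the trial's main purpose.

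**What to change.** **If enrolment is open.** Amend section 5.5 so that study staff give the three scales to every Veteran at the consent and baseline visit. Use those scores as the baseline, and keep chart scores as descriptive only.

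**If enrolment is complete,** report:
1. The number of chart baselines and the interval from score date to first session.
2. Pre-to-post change with 95% confidence intervals separately by baseline source, noting that Veterans with staff-administered baselines may differ from recent clinic admissions.
3. Change from post-Module 1 to post-Module 2, which uses no chart score, noting that it misses Module 1 effects.

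For Veterans in the optional EMA study, change from the baseline burst can be shown alongside as supportive only, since it is opt-in and uses different items. In either case, change the baseline rule in the planned RCT.

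**Cost.** 22 + 9 + 7 = 38 items, once, for clinic recruits (seven for the GAD-7 is taken from its name). The visit is already paid and carries seven scales plus AIM, IAM and FIM. The burden saving that the protocol sought is lost.

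The split by source is imprecise: with 18 Veterans the half-width is 2.11 × 0.9/√18 = 0.45 SD (0.35 to 0.65 for SD 0.7 to 1.3). It also compares different populations, so it cannot isolate score age. Fresh baselines remove only the chart increment. At drift 0.2 continuing through treatment, with half on 13-week-old scores, 61% falls to 36%, not to 5%.

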Based on adaptations from existing recovery-based and COVID-19 distress group interventions that our team has developed/piloted, we have developed a treatment framework that consists of twenty 75-minute weekly sessions. The therapy will be divided into two modules consisting of 8 sessions each (16 sessions total): Module 1 (the first 8 sessions) will target more immediate symptoms and Long-COVID related issues as part of the recovery process. Module 2 (the second 8 sessions) will focus on more long-term recovery and creating a meaningful and purposeful future. We specifically are designing a group intervention to build support and mitigate the loneliness associated with chronic conditions such as Long-COVID. The core sessions will focus on the impact of Long-COVID on mental and physical health, teach coping skills to foster resiliency and hope, identify barriers to employment/education due to Long-COVID, and review relapse prevention.

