## 5.0 Study Procedures

## 5.1 Study Design

**Group Intervention.** Veterans will participate in a LC-CR group (75 minutes 1x/week for a total of 16 sessions) via the HIPAA-compliant telehealth platform VA Video Connect (VVC) in accordance with the Office of Connected Care (OCC)'s best telehealth practices. VA WebEx will be available as an approved back-up telehealth platform in the event of VVC technical difficulties.

The intervention will be delivered in two modules consisting of 8 sessions each (16 sessions total):

**Module 1:** The first 8 sessions of the treatment will focus on skill based coping strategies to target more immediate symptoms and Long-COVID related issues as part of the recovery process.

**Module 2:** The second 8 sessions will focus on more long-term recovery and creating a meaningful and purposeful future.

Sessions will be co-facilitated by [name] and another co-therapist. [name] will be the co-therapist for Module 1 of therapy (first 8 sessions) and [name] will be the co-therapist for Module 2 of therapy (second 8 sessions).

**Timeline:** (See **GANTT chart**) For the first 3 months we will complete the needs assessment interviews. In months 4-7, we will revise the psychotherapy workbook and therapist manual *and will consult with stakeholders monthly for input on revisions throughout our piloting phases*. In months 18-24, we will develop and submit a RR&D Merit grant application for an RCT to test the treatment.

Project dates: 10/1/22- 9/30/24	Year 1				Year 2			
	Q1	Q2	Q3	Q4	Q1	Q2	Q3	Q4
Activity	October - December (2022)	January-March (2023)	April-June (2023)	July-September (2023)	October-December (2023)	January-March (2024)	April-June (2024)	July-September (2024)
IRB								
Train RA and other startup activities								
Complete PACS needs assessment								
Analyze needs assessment results								
Finish developing psychotherapy materials and therapist manual								
Consult with stakeholders on proposed intervention and revise materials								
Run first set of pilot group								
Revise treatment based on trial participants and stakeholder feedback								
Run second set of pilot groups								
Present findings								
manuscript preparation								
Merit preparation/sSubmission								

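### The two figures in the clinician-hours target (100 per cycle, 5 per group) agree at 20 sessions but not at 16, if the smaller one is hours per group session

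*Protocol*

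**What the plan says.** Protocol section 5.5, in the paragraph on feasibility and acceptability metrics, makes implementation ease the first of three feasibility measures. It is assessed by "tracking the hours clinicians spend in preparation, delivery, and supervision", "with a target of 100 hours/ cycle (5 hours per group"). The units *group* and *cycle* are not defined there or elsewhere in the text available.

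The session count appears in several places:

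- Section 2.0: "we have developed a treatment framework that consists of twenty 75-minute weekly sessions".
- Section 2.0, next sentence: "The therapy will be divided into two modules consisting of 8 sessions each (16 sessions total").
- Section 5.1: "75 minutes 1x/week for a total of 16 sessions".
- Section 5.5, retention criteria in the same paragraph as the hours target: "10 of the total 16 sessions (Module 1 + Module 2").

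The module bonuses in section 5.2 and the assessment timing in section 5.5 also rest on 8 + 8 sessions. Section 5.1 gives each session two facilitators ("Sessions will be co-facilitated by" two named clinicians), but section 5.5 does not say whether both clinicians' hours count. The SAP does not mention clinician hours.

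**The concern.** The figure in parentheses looks like the unit rate from which the 100 hours was built. If so, rate times number of units should return 100. At the session count used in nearly every part of the protocol, it does not.

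Assessing acceptability and feasibility is the overall goal in section 3.0, and section 5.6 says the data will be used to examine both and to improve the treatment. The hours target is the only numeric benchmark for its measure. With two figures that disagree, the same observed total can look favourable against one and unfavourable against the other. For example, if the target is a ceiling (the protocol does not say so), a 16-session cycle using more than 80 and up to 100 hours meets the per-cycle figure and exceeds the per-session one.

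**Working it through.** **Inputs.** Target per cycle 100 h and rate 5 h per group (section 5.5). Sessions: 20 (section 2.0, first statement) or 16 (section 2.0, next sentence; section 5.1; section 5.5). Session length 75 min = 1.25 h (sections 2.0 and 5.1). Maximum enrolment 36 (section 5.2).

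**Reproducing the stated figure, with *group* read as a group session.** Hours per cycle = hours per session × sessions.

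- Implied number of sessions: 100 / 5 = 20.
- At 20 sessions: 20 × 5 = 100 h. Reproduced exactly.
- At 16 sessions: 16 × 5 = 80 h. Not reproduced.
- Gap at 16 sessions: 100 − 80 = 20 h, which is 20 / 100 = 20% of the target, or 20 / 16 = 1.25 h per session.
- Rate needed to keep 100 h at 16 sessions: 100 / 16 = 6.25 h per session.

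**Readings that do not give 100 h.**

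- *Group* as a whole pilot group, as in the timeline entry "Run second set of pilot groups": delivery alone takes 16 × 1.25 = 20 h, already above 5 h. It would also take 100 / 5 = 20 groups in one cycle, or 36 / 20 = 1.8 Veterans each at maximum enrolment.
- *Cycle* as one 8-session module: 8 × 5 = 40 h.
- 5 h for each of two facilitators: 16 × 5 × 2 = 160 h.

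**Readings that reach 100 h at 16 sessions.** Each needs an element that the documents do not state.

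- A fixed allowance outside sessions: 80 + 20 = 100 h. No 20 h allowance appears.
- One therapist's delivery time added to the 5 h: 16 × 5 + 16 × 1.25 = 80 + 20 = 100 h. This fits poorly, because delivery is already among the activities that the target covers.
- A weekly rate for a running group: 5 h × 20 weeks = 100 h. Sixteen weekly sessions fill 16 weeks, so the cycle would need about 4 further weeks. The text states no such cycle length. The cells of the timeline chart could not be read in the copy available, so nothing that they may show is counted as missing.

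**The case against.** The strongest reply is that the mismatch depends on a word the protocol does not use. It says hours per group, not per session, and the same paragraph uses *session* freely when it means a meeting. Elsewhere *group* often means the cohort or the programme. What the text establishes most firmly is therefore an undefined unit. An arithmetic error follows only under an inferred reading, and three other readings reach 100 hours at 16 sessions. This stands, and it limits the point. It does not remove it: each of the three needs an unstated quantity, so the target cannot be applied as written under any of them, and much the same clarification is needed.

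A second reply is that this is a by-product of the 20-versus-16 contradiction in section 2.0. That is probably right. The exact agreement at 20 is the best evidence for the per-session reading, and the two corrections belong together. The hours target still needs its own edit, because correcting section 2.0 would not by itself define the unit or align the two figures.

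A third reply is that little turns on the figure. This also stands. Section 5.5 labels only retention and recruitment as adequate or not, and sets no such rule for hours.

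A reader might infer that the match at 20 proves the target was left over from a 20-session course, or that the study's feasibility conclusion is compromised. The documents support neither. The match is suggestive only, and no feasibility decision is tied to hours.

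**Conclusion.** The point holds as a minor inconsistency, with medium confidence. If the 5 hours is a rate per group session covering all the tracked activities, the target is consistent at 20 sessions. At 16 sessions it is out by 20 hours per cycle: 80 against 100 hours, or 5 against 6.25 hours per session. The conclusion rests on that reading, which is the most natural one but is not stated, and on no unstated allowance being intended.

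The effect is confined to one feasibility benchmark. No primary or secondary outcome analysis depends on it. The documents do not settle which session count is intended, and nothing here takes a side on that; the passages have to be reconciled.

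**What to change.** 1. Reconcile the session count across section 2.0, section 5.1 and the metrics paragraph of section 5.5.
2. Restate the hours target so that its per-cycle and per-unit figures agree for the reconciled count. Define *group* and *cycle*, and say whether both facilitators' hours and any hours outside sessions are included. If an allowance or a longer cycle was intended, state it.
3. The SAP is written in the past tense, so cycles may already have been run. In that case, report observed hours per cycle and per session against both stated figures and disclose the discrepancy, rather than choosing one figure after the hours are known.

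The cost is small: text edits in sections 2.0 and 5.5, made together with the session-count correction, and, if cycles are complete, one disclosure sentence and a comparison with both figures in the report. The protocol already plans to track the hours, so no new data collection is needed.
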